2.3 Other Endpoints and Analysis Methodology

2.3.1 Fasting C-peptide, Fasting Glucagon, DPP-4 Activity, Weight

Analysis set:	Full analysis set
Analysis variables:	Fasting C-peptide Fasting glucagon DPP-4 activity Weight
Visits:	Fasting C-peptide Weeks -6, -2, 0, 2, 4, 8, 12, 24, 36, 52, 54, at the end of Treatment Period I, and at the end of Treatment Period II Fasting glucagon, DPP-4 activity Weeks 0, 2, 4, 8, 12, 24, 36, 52, 54, at the end of Treatment Period I, and at the end of Treatment Period II Weight Weeks -6, -2, 0, 2, 4, 8, 12, 16, 20, 24, 28, 32, 36, 40, 44, 48, 52, 54, at the end of Treatment Period I, and at the end of Treatment Period II
Analysis methodology:	The following analyses (1) and (2) will be performed for the above analysis variables. For the mean and standard deviation plot, a plot until Treatment Period I and a plot for the entire study will be created respectively and the plot for the entire period will not be output at Week 54 and at the end of Treatment Period I. (1) Summary statistics and the two-sided 95% CI for the mean will be calculated for each visit and the mean and standard deviation plot by treatment group will be prepared. Also, the intergroup difference in the mean between treatment groups (SYR-472 25 mg/SYR-472 25 mg group – placebo/SYR-472

25 mg group) and the two-sided 95% CI will be calculated for each visit during the Screening and Treatment Period I.

(2) The same analysis as the above (1) will be performed for changes from Week 0 at each visit after Treatment Period I (for DPP-4 activity, inhibition rate $[100 \times (\text{Week 0} - \text{each visit after Treatment Period I}) / \text{Week 0}]$, rounded off to the first decimal place]).

2.4 Statistical and Analytical Issues

2.4.1 Adjustments for Covariates

See 2.1.1 Primary Analysis.

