13.0 STATISTICAL METHODS

13.1 Statistical and Analytical Plans

A statistical analysis plan (SAP) will be prepared and finalized prior to unblinding of subject's treatment assignment. This document will provide further details regarding the definition of analysis variables and analysis methodology to address all study objectives.

A blinded data review will be conducted prior to unblinding of subject's treatment assignment. This review will assess the accuracy and completeness of the study database, subject evaluability, and appropriateness of the planned statistical methods.

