13.1.3 Efficacy Analysis

(1) Primary endpoint and analytical methods

[Primary endpoint]

Change in HbA1c at the end of Treatment Period I from the end of the screening period (Week 0)

[Primary analysis]

The following analyses will be performed in the FAS.

The population mean change in HbA1c at the end of Treatment Period I from the end of the screening period (Week 0) will be compared between SYR-472 25 mg group and placebo group based on an analysis of covariance (ANCOVA) model for the change in HbA1c at the end of Treatment Period I from the end of the screening period (Week 0) with factors of treatment group and HbA1c at the end of the screening period (Week 0).

The same ANCOVA model will be used to calculate the least square (LS) mean and the two-sided 95% confidence interval (CI) for each treatment group, as well as the intergroup difference in the LS mean between the treatment groups (SYR-472 25 mg group - placebo group) and the two-sided 95% CI.

[Secondary analysis]

For the change in HbA1c at the end of Treatment Period I from the end of the screening period (Week 0), summary statistics (number of subjects, mean, standard deviation, maximum, minimum, and quartiles; hereinafter the same) and two-sided 95% CI for the mean will be calculated for each treatment group, as well as the intergroup difference in the mean between treatment groups (SYR-472 25 mg group - placebo group) and the two-sided 95% CI.

In addition, the same analyses as the primary analysis and the secondary analysis described above will be performed using the PPS to evaluate the robustness of the results in terms of a sensitivity analysis.

[Adjustment for covariates]

The following analyses will be performed in the FAS.

The treatment effect of SYR-472 25 mg will be assessed in consideration of the effects of baseline characteristics based on the ANCOVA model for the change in HbA1c at the end of Treatment Period I from the end of the screening period (Week 0) with factors of treatment group, HbA1c at the end of the screening period (Week 0) and baseline characteristics that may affect the primary endpoint at the blind data review.

(2) Secondary Endpoints and Analysis Methods

[Secondary endpoints]

HbA1c, fasting blood glucose, glycoalbumin

[Analytical methods]

The following analyses will be performed in the FAS.

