1.2 Demographic and Other Baseline Characteristics

1.2.1 Distribution of Baseline Demographics

Analysis set:	All subjects who were randomized	
Analysis variables:	Age (years)	[Min \leq - <65, 65 \leq - \leq Max]
		[Min \leq - <75, 75 \leq - \leq Max]
	Sex	[Male, Female]
	Height (cm)	
	Weight (kg) (Week 0)	
	BMI (kg/m ²) (Week 0)	[Min \leq - <18.5, 18.5 \leq - <25.0, 25.0 \leq - <30.0, 30.0 \leq - \leq Max]
	Duration of disease (months)	[Min \leq - \leq 24, 24< - \leq 60, 60< - \leq 120, 120< - \leq Max]
	Smoking status	[Never smoked, Current smoker, Ex-smoker]
	Alcohol use	[Yes, No]

Exercise therapy	[Yes, No]
Hemodialysis	[Yes (end-stage renal failure), No (severe renal impairment)]
Use of antidiabetic drugs (Week -6)	[Yes, No]
Rapid-acting insulin	[Yes, No]
secretagogues	
Details of rapid-acting insulin secretagogues	
Mitiglinide calcium hydrate	[Yes]
Repaglinide	[Yes]
α -glucosidase inhibitors	[Yes, No]
Details of α -glucosidase inhibitors	
Acarbose	[Yes]
Miglitol	[Yes]
Voglibose	[Yes]
Insulin preparations	[Yes, No]
Types of insulin preparations	[Mixed, intermediate-acting, Long-acting soluble]
Reason for concomitant use of antidiabetic drugs being judged to be appropriate	[Combination therapy is expected to be more effective, Development of AEs due to dose increase is concerned, Maximum dose has already been administered, Other]
Creatinine (mg/dL) (Week 0)	Male
Male	[Min \leq - \leq 2.4, 2.4 $<$ - \leq Max]
Female	Female
	[Min \leq - \leq 2.0, 2.0 $<$ - \leq Max]
Creatinine clearance (mL/min) (Week 0)	
eGFR (mL/min/1.73 m ²) (Week 0)	[Min \leq - $<$ 15, 15 \leq - $<$ 30, 30 \leq - \leq Max]
HbA1c (%) (Week 0)	[Min \leq - $<$ 7.0, 7.0 \leq - \leq Max]
	[Min \leq - $<$ 8.0, 8.0 \leq - \leq Max]

Fasting blood glucose (mg/dL) (Week 0)	[Min≤ - <130, 130≤ - <160, 160≤ - ≤Max]
Glycoalbumin (%) (Week 0)	[Min≤ - <24, 24≤ - ≤Max]
Fasting C-peptide (ng/mL) (Week 0)	[Min≤ - <1.0, 1.0≤ - <2.0, 2.0≤ - ≤Max]
Fasting glucagon (pg/mL) (Week 0)	
DPP-4 activity (nmol/min/mL) (Week 0)	
Analysis methodology:	The following analysis will be performed for the above analysis variables by each treatment group and in the consolidated treatment groups. (1) Frequency distributions for categorical variables and summary statistics for continuous variables

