2.1 Primary Endpoints and Analysis Methodology

2.1.1 Primary Analysis

Analysis set: Full analysis set

Analysis variables: Change in HbA1c at the end of Treatment Period I from Week 0

Analysis methodology: The population mean change in HbA1c at the end of Treatment Period I from Week 0 will be compared between the SYR-472 25 mg/SYR-472 25 mg group and placebo/SYR-472 25 mg group based on an analysis of covariance (ANCOVA) model for the change in HbA1c at the end of Treatment Period I from Week 0 with factors of treatment group and HbA1c at Week 0. The same ANCOVA model will be used to calculate the least square (LS) mean and the two-sided 95% confidence interval (CI) for each treatment group, as well as the intergroup difference in the LS mean between the treatment groups (SYR-472 25 mg/SYR-472 25 mg group – placebo/SYR-472 25 mg group) and the two-sided 95% CI.

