2.4.8 Examination of Subgroups

Analysis set:	Full analysis set
Analysis variables:	Change in HbA1c at the end of Treatment Period I from Week 0
Stratum:	
Age (years) [Min≤ - <65, 65≤ - ≤Max]
 
Sex [Male, Female]
 
BMI (kg/m²) (Week 0) [Min≤ - <25.0, 25.0≤ - <30.0, 30.0≤ - ≤Max]
 
Duration of disease (months) [Min≤ - ≤120, 120< - ≤Max]
 
Medication history [Yes, No]
 
Hemodialysis [Yes (end-stage renal failure), No (severe renal impairment)]

	
Use of antidiabetic drugs (Week -6) [Yes, No]
 
Rapid-acting insulin secretagogues [Yes, No]
 
α-glucosidase inhibitors [Yes, No]
 
Insulin preparations [Yes, No]

	
eGFR (mL/min/1.73 m²) (Week 0) [Min≤ - <15, 15≤ - ≤Max]
 
HbA1c (%) (Week 0) [Min≤ - <7.0, 7.0≤ - ≤Max] [Min≤ - <8.0, 8.0≤ - ≤Max]
 
Fasting blood glucose (mg/dL) [Min≤ - <160, 160≤ - =Max] (Week 0)

	
Glycoalbumin (%) (Week 0) [Min≤ - <24, 24≤ - ≤Max]
 
Fasting C-peptide (ng/mL) [Min≤ - <2.0, 2.0≤ - ≤Max] (Week 0)

Analysis methodology:	
The following analyses will be performed for the above analysis variables.
 
(1) Summary statistics and the two-sided 95% CI for the mean will be calculated for each stratum by treatment group, as well as the intergroup difference in the mean between treatment groups (SYR-472 25 mg/SYR-472 25 mg group – placebo/SYR-472 25 mg group) and the two-sided 95% CI.
 
(2) The ANCOVA will be performed for each stratum with the change in HbA1c at the end of Treatment Period I from Week 0 as the response and with treatment group, stratum, and

interactions of treatment group and stratum as factors. The stratum will be included in the ANCOVA model as category variables based on the above category and analyzed.

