	
...
 
Also, regarding the presence or absence of any change in doses of antidiabetic drugs that are being used at Week -6 and will be concomitantly used during the study period in Treatment Period II, ...
	
...
 
Also, regarding the presence or absence of any change in antidiabetic drugs that are being used at Week -6 and will be concomitantly used during the study period in Treatment Period II, ...
	
27	
2.4.8 Examination of Subgroups
 
Duration of disease (months)
 
[Min≤ - ≤60, 60< - =Max]
 
Fasting C-peptide (ng/mL)
 
[Min≤ - <1.0, 1.0≤ - <2.0, 2.0≤ - ≤Max]
	
2.4.8 Examination of Subgroups
 
Duration of disease (months)
 
[Min≤ - ≤120, 120< - =Max]
 
Fasting C-peptide (ng/mL)
 
[Min≤ - <2.0, 2.0≤ - ≤Max]
	Changes in the contents of distributions as a result of reexamination of categories at the blinded review
29	
3.1.2 3.1.2 Displays of Treatment-Emergent Adverse Events
	
3.1.2 3.1.2 Displays of Treatment-Emergent Adverse Events
 
(19) Hypoglycemia-related TEAEs by SOC and PT
	Addition of distributions as a result of reexamination of contents of distributions

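### Does SAP 2.4.1 drop the covariate-adjusted ANCOVA that protocol 13.1.3 plans?

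*SAP*

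**What the plan says.** Protocol 13.1.3 treats the primary endpoint, change in HbA1c from Week 0 to the end of Treatment Period I, in three places. The primary analysis is an ANCOVA with treatment and Week 0 HbA1c. The secondary analysis gives unadjusted summaries and repeats both analyses in the per protocol set. A third heading, on adjustment for covariates, plans an ANCOVA in the full analysis set with the same two terms plus "baseline characteristics that may affect the primary endpoint at the blind data review".

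Protocol 13.1 describes the SAP's task: "This document will provide further details regarding the definition of analysis variables and analysis methodology to address all study objectives". It also places both the SAP's finalization and the blinded data review before unblinding.

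SAP 2.1.1 gives the primary model, "with factors of treatment group and HbA1c at Week 0". SAP 2.4.1, headed as covariate adjustment, consists of one sentence: "See 2.1.1 Primary Analysis". No other SAP section lists covariates for an extended model. The change table in SAP Appendix 1 has no entry on covariates, although for the subgroup categories it gives the reason "Changes in the contents of distributions as a result of reexamination of categories at the blinded review".

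**The concern.** The SAP heading that should carry the extended model leads back to the model the protocol meant to extend. An analyst working from the SAP alone would not fit the adjusted analysis and would find no note that it had been withdrawn. The second SAP version (12 June 2018) already refers to the blinded review, so a covariate decision could have been recorded there.

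Two things seem to be at stake. One is the protocol's check that the treatment effect holds after allowing for other baseline characteristics. That check has some appeal in a small trial mixing dialysis and non-dialysis subjects under different HbA1c entry rules. The other is the evidence that covariates were chosen blind. Without a dated list, a later adjusted result could be suspected of having been picked from several.

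**Working it through.** **1. The plan's power figure, and which model it concerns.** Inputs from protocol 13.3: difference 0.40, SD 0.80, 51 evaluable per group, two-sided 5% two-sample t-test. The noncentrality is (0.40/0.80) × √(51/2) = 2.525 on 2 × 51 − 2 = 100 degrees of freedom. Exact power is 70.56%, which reproduces the stated 70.6%. The original 86 per group also reproduces: 90.3% at 86 and 89.99% at 85. These figures belong to the primary comparison, and the covariate section has no part in them.

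**2. The two documents side by side.**

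| Item | Protocol 13.1.3 | SAP |
|---|---|---|
| Primary model | Treatment, Week 0 HbA1c | Same (2.1.1) |
| Primary analysis set | Full analysis set | Same |
| Per protocol repeat | Yes | Yes (2.1.2) |
| Extended ANCOVA: endpoint, set, form | Fixed | Not restated, not withdrawn |
| Extended ANCOVA: covariate names | Left to the blind data review | Not given |

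Only the last two rows differ. What neither document supplies is the list of covariate names.

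**3. What follows in each case.**
- The review chose no covariate. The extended model then reduces to treatment plus Week 0 HbA1c, which is SAP 2.1.1, and the pointer is right.
- The review chose covariates. The protocol's model still applies, and the analyst takes the names from the review record.
- The analysis was dropped. A supporting result is missing, which is a departure from the protocol to report. The primary result stands.

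The primary estimate, interval and test are the same in all three.

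**4. What the SAP provides nearby.** SAP 1.2.1 tabulates baseline characteristics by arm, including hemodialysis. SAP 2.4.8(1) covers within-stratum results: "Summary statistics and the two-sided 95% CI for the mean will be calculated for each stratum by treatment group", with the difference between arms and its interval. SAP 2.4.8(2) fits treatment, stratum and "interactions of treatment group and stratum as factors". These models omit Week 0 HbA1c as a separate covariate and yield no single adjusted effect, so they do not replace the extended model. They do show balance between arms and whether the effect differs by stratum.

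**5. How far an omitted covariate could move the primary estimate.** The documents give no inputs, so these are assumed for hemodialysis: share p of 30–50%, gap g of 0.2–0.4 HbA1c points at equal Week 0 HbA1c, squared correlation ρ² with Week 0 HbA1c of 0–0.25, and R² of Week 0 HbA1c of 0–0.2. A one-SD chance imbalance shifts the estimate by g × √(2 p(1−p)(1−ρ²)/51).
- Lowest: 0.2 × √(2 × 0.21 × 0.75/51) = 0.016.
- Highest: 0.4 × √(2 × 0.25/51) = 0.040.
- The standard error is 0.80 × √(2/51) = 0.158 at R² = 0, and 0.158 × √0.8 = 0.142 at R² = 0.2. The shift is therefore 0.10–0.28 standard errors.
- At 1.96 SD the shift is 0.03–0.08 points, or 0.19–0.55 standard errors.

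Under randomization, chance imbalance of this kind is already part of the sampling error that the primary standard error reflects. It does not bias the primary test.

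**The case for a change.** The strongest case for a change is that the protocol says this analysis will be done and gives the methods detail to the SAP, yet the SAP is silent. Neighbouring SAP sections say plainly what will not be done: no interim analysis (2.4.3), no site interaction, with a reason (2.4.4), and no equivalence question (2.4.7). Where the SAP relies on the Handling Rules for Analysis Data it names them, and 2.4.1 does not. One sentence would have settled the matter. All of this stands as a point about traceability.

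The case for harm is weaker. SAP 2.4.8 lists 14 baseline characteristics other than HbA1c, giving 14 one-covariate and 91 two-covariate models, 105 in all. In a null simulation with independent covariates, reporting the smallest p-value was significant in 7.9% of trials over the 14 models and 9.8% over the 105, against 5.3% for the primary model. Neither document permits such a search. The protocol ties selection to the blind review, and the SAP as written authorizes no adjusted model to choose among. The 14 come from a subgroup list, not a covariate list. They are also not independent: entry criterion 7 allows at most one antidiabetic drug, so overall drug use is the sum of the three drug-class indicators.

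Adding hemodialysis as a covariate would gain 0.4 to 3.1 percentage points of power on the assumed inputs above. That gain belongs to a model other than the primary one. The choice of covariates is also the blind review's to make.

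**Conclusion.** No change follows. The SAP does not carry forward one sentence of the protocol. What is missing is a list of covariate names for one supporting analysis, or a note that there are none. An analyst holding both documents can fill the gap from the blinded review record.

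The effect on the primary analysis is nil: model, analysis set, test, interval and the 70.6% power are unaffected. SAP 2.4.5 rests the conclusion on that analysis and reads everything else as support or exploration.

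This rests on two assumptions that the documents cannot confirm. The first is that any covariates were fixed at the blinded review. Appendix 1 shows that the review took place but says nothing about covariates, and neither the review record nor the Handling Rules is available here. The second is that an adjusted result, if reported, is presented as supporting only. A reader who meets an adjusted result without a dated covariate list should give it little weight, and that caution does not extend to the primary result.

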2.4.2 Handling of Dropouts or Missing Data

Missing test results and ineligible data according to the “Handling Rules for Analysis Data” or the SAP will be excluded from statistical analyses and estimations.

2.4.3 Interim Analysis and Data Monitoring

No interim analysis is planned.

2.4.4 Multicenter Studies

Although this is a multicenter study, interactions between treatment and the study site will not be investigated since the target number of subjects per study site is not sufficiently large for meaningful analyses of the interactions.

2.4.5 Multiple Comparisons/Multiplicity

The main focuses will be placed on the results of the primary analysis performed for the primary endpoint defined as “change in HbA1c at the end of Treatment Period I from Week 0” in the “full analysis set.” Other analytical results will be interpreted to support the results of the primary endpoint or to explore the characteristics of efficacy of the study drug. These results will be considered one measure suggesting the trends or characteristics of efficacy. Thus, no adjustment for multiplicity will be performed.

2.4.6 Use of an “Efficacy Subset of Subjects”

To confirm the robustness of the primary analysis results for the primary endpoint for the sensitivity point of view, the same analysis as for the “full analysis set” will be performed secondarily in the “per protocol set.”

2.4.7 Active-Control Studies Intended to Show Equivalence or Non-inferiority

Not applicable.

2.4.8 Examination of Subgroups

Analysis set:	Full analysis set
Analysis variables:	Change in HbA1c at the end of Treatment Period I from Week 0
Stratum:	
Age (years) [Min≤ - <65, 65≤ - ≤Max]
 
Sex [Male, Female]
 
BMI (kg/m²) (Week 0) [Min≤ - <25.0, 25.0≤ - <30.0, 30.0≤ - ≤Max]
 
Duration of disease (months) [Min≤ - ≤120, 120< - ≤Max]
 
Medication history [Yes, No]
 
Hemodialysis [Yes (end-stage renal failure), No (severe renal impairment)]

	
Use of antidiabetic drugs (Week -6) [Yes, No]
 
Rapid-acting insulin secretagogues [Yes, No]
 
α-glucosidase inhibitors [Yes, No]
 
Insulin preparations [Yes, No]

	
eGFR (mL/min/1.73 m²) (Week 0) [Min≤ - <15, 15≤ - ≤Max]
 
HbA1c (%) (Week 0) [Min≤ - <7.0, 7.0≤ - ≤Max] [Min≤ - <8.0, 8.0≤ - ≤Max]
 
Fasting blood glucose (mg/dL) [Min≤ - <160, 160≤ - =Max] (Week 0)

	
Glycoalbumin (%) (Week 0) [Min≤ - <24, 24≤ - ≤Max]
 
Fasting C-peptide (ng/mL) [Min≤ - <2.0, 2.0≤ - ≤Max] (Week 0)

Analysis methodology:	
The following analyses will be performed for the above analysis variables.
 
(1) Summary statistics and the two-sided 95% CI for the mean will be calculated for each stratum by treatment group, as well as the intergroup difference in the mean between treatment groups (SYR-472 25 mg/SYR-472 25 mg group – placebo/SYR-472 25 mg group) and the two-sided 95% CI.
 
(2) The ANCOVA will be performed for each stratum with the change in HbA1c at the end of Treatment Period I from Week 0 as the response and with treatment group, stratum, and

interactions of treatment group and stratum as factors. The stratum will be included in the ANCOVA model as category variables based on the above category and analyzed.

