**: Any of the following insulin monotherapies: mixed (rapid-acting or ultrarapid-acting insulin containing no more than 30% of volume), intermediate-acting, or long-acting soluble insulin preparations
- 8. The subject is not undergoing hemodialysis or peritoneal dialysis and has severe renal impairment (creatinine clearance [Ccr] <30 mL/min at the start of the screening period [Week -6]), or the subject is undergoing hemodialysis and has end-stage renal failure.
- 9. In the opinion of the investigator or sub-investigator, the initiation of hemodialysis or peritoneal dialysis within 12 weeks after initiation of the study drug is not expected. (in cases where the subject is not undergoing hemodialysis or peritoneal dialysis [patients with severe renal impairment])
- 10. The subject has been undergoing hemodialysis started from at least 6 months prior to informed consent and, in the opinion of the investigator or sub-investigator, the subject is clinically stable. (in cases where the subject is undergoing hemodialysis [patient with end-stage renal failure])
- 11. The subject is male or female and is aged 20 years or older at the time of informed consent.
- 12. A female subject of childbearing potential who is sexually active with a nonsterilized male partner agrees to routinely use adequate contraception from signing of informed consent until 1 month after the end of the study.
- 13. In the opinion of the investigator or sub-investigator, the subject is capable of understanding and complying with protocol requirements.
- 14. The subject signs and dates a written, informed consent form prior to the initiation of any study procedures.

Criteria for Exclusion:

1. The subject has clinically evident hepatic impairment (e.g., AST or ALT ≥ 2.5 times the upper limit of normal or total bilirubin of ≥ 2.0 mg/dL at the start of the screening period [Week -6] or at Week -2 of the screening period).
2. The subject has any serious cardiac diseases, cerebrovascular disorders, or serious pancreatic or hematological diseases (e.g., subjects who require inpatient treatment or had been hospitalized for treatment within 24 weeks prior to the start of the screening period).
3. The subject has severe ketosis, diabetic coma or pre coma, type 1 diabetes, severe infection, or severe external injury, or is immediately before or after surgery.
4. The subject has hemoglobinopathy (sickle cell disease, thalassemia, etc.).

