**: Any of the following insulin monotherapies: mixed (rapid-acting or ultrarapid-acting insulin containing no more than 30% of volume), intermediate-acting, or long-acting soluble insulin preparations
- 8. The subject is not undergoing hemodialysis or peritoneal dialysis and has severe renal impairment ($\text{Cr} < 30 \text{ mL/min}$ at the start of the screening period [Week -6]), or the subject is undergoing hemodialysis and has end-stage renal failure.
- 9. In the opinion of the investigator or sub-investigator, the initiation of hemodialysis or peritoneal dialysis within 12 weeks after the initiation of the study drug is not expected. (in cases where the subject is not undergoing hemodialysis or peritoneal dialysis [patients with severe renal impairment])
- 10. The subject has been undergoing hemodialysis started from at least 6 months prior to informed consent and, in the opinion of the investigator or sub-investigator, the subject is clinically stable. (in cases where the subject is undergoing hemodialysis [patient with end-stage renal failure])
- 11. The subject is male or female and is aged 20 years or older at the time of informed consent.
- 12. A female subject of childbearing potential who is sexually active with a nonsterilized male partner agrees to routinely use adequate contraception from signing of informed consent until 1 month after the end of the study.

Definitions and acceptable methods of contraception are defined in Section 9.1.10 Contraception and Pregnancy Avoidance Procedure and reporting responsibilities are defined in Section 9.1.11 Pregnancy.

- 13. In the opinion of the investigator or sub-investigator, the subject is capable of understanding and complying with protocol requirements.
- 14. The subject signs and dates a written, informed consent form prior to the initiation of any study procedures.

<Justification of Inclusion Criteria>

1. The criterion was set as the target disease of the study.
2. In order to select subjects who maintain capacity for secreting intrinsic insulin, the lower limit of the fasting C-peptide value was set at 0.6 ng/mL based on Training Guidebook for Board Certified Diabetologists (the revised 6th edition)[6].

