9.0 STUDY PLAN

9.1 Study Procedures

The following sections describe the study procedures and data to be collected. For each procedure, subjects are to be assessed by the same investigator or sub-investigator whenever possible. The Schedule of Study Procedures is located in Appendix A.

If a subject undergoing hemodialysis (patients with end-stage renal failure) receive hemodialysis on the day of study site visit, all procedures should be performed before hemodialysis.

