- Creatinine clearance (mL/min): To be calculated using the following Cockcroft-Gault equation (rounded off to the nearest integer in both cases).

Male: $([140 - \text{Age}] \times \text{Weight [kg]}) / (72 \times \text{Serum creatinine [mg/dL]})$

Female: $0.85 \times ([140 - \text{Age}] \times \text{Weight [kg]}) / (72 \times \text{Serum creatinine [mg/dL]})$

Creatinine clearance will be calculated when the variables to be used for calculation are all evaluable and measured on the same day. The age will be calculated from the test dates of variables to be used for calculation and the date of birth.
- eGFR (mL/min/1.73 m²): To be calculated using the following equation (rounded off to the nearest integer in both cases).

Male: $194 \times \text{Serum creatinine (mg/dL)}^{-1.094} \times \text{Age}^{-0.287}$

Female: $194 \times \text{Serum creatinine (mg/dL)}^{-1.094} \times \text{Age}^{-0.287} \times 0.739$

The age will be calculated from the test dates of variables to be used for calculation and the date of birth.
- Duration of disease (months): Period from the onset time of type 2 diabetes until the time of informed consent.
- Duration of study drug exposure for Treatment Period I: Date of the last administration of the study drug for Treatment Period I – Date of the start of the study drug administration for Treatment Period I + 1
- Compliance with study drug for Treatment Period I: Number of study drug administrations for Treatment Period I / (Smallest integer of \geq [(Date of the last administration of the study drug for Treatment Period I – Date of the start of the study drug administration for Treatment Period I + 7) / 7]) $\times 100$ (rounded off to the first decimal place)
- Duration of exposure to SYR-472 25 mg tablet: Date of the last administration of SYR-472 25 mg tablet – Date of the start of SYR-472 25 mg tablet + 1
- Compliance with SYR-472 25 mg tablet: Number of administrations of SYR-472 25 mg tablet / (Smallest integer of \geq [(Date of the last administration of SYR-472 25 mg tablet – Date of the start of SYR-472 25 mg tablet + 7) / 7]) $\times 100$ (rounded off to the first decimal place)

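### The eGFR subgroup (below 15 vs 15 or above) in SAP 2.4.8 and 3.1.3 is not separated from hemodialysis status, so its contrast is confounded with dialysis to a degree the documents do not fix

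*SAP*

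**What the plan says.** SAP 2.4.8 examines the HbA1c change at the end of Treatment Period I by subgroup in the full analysis set. One factor is "eGFR (mL/min/1.73 m²) (Week 0) [Min≤ - <15, 15≤ - ≤Max". SAP 3.1.3 uses the same cut for TEAEs in the safety analysis set. Both lists also carry "Hemodialysis [Yes (end-stage renal failure), No (severe renal impairment" as a separate factor. The model in 2.4.8 (2) takes one factor at a time, with treatment, the factor and their interaction; 3.1.3 tabulates one factor at a time.

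The SAP's Other Handling list defines eGFR from serum creatinine, age and sex: "To be calculated using the following equation (rounded off to the nearest integer in both cases". It makes no exception for dialysed subjects.

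The protocol classes the two populations differently. Under inclusion criterion 8, a non-dialysed subject enters on "creatinine clearance [Ccr] <30 mL/min at the start of the screening period [Week -6" (wording of the Study Summary), with no lower limit. The alternative route is that "the subject is undergoing hemodialysis and has end-stage renal failure", with no creatinine or clearance range. Protocol 9.1 adds that when dialysis falls on a visit day "all procedures should be performed before hemodialysis". The clearance-based discontinuation rule in Protocol 7.5 is confined to subjects not on hemodialysis.

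**The concern.** In a dialysed subject, serum creatinine depends on dialysis as well as on the kidney, so an eGFR computed from it has no clear renal-function meaning. Placing these subjects in a renal-function subgroup together with non-dialysed subjects joins two populations that the entry criteria keep apart.

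If dialysed subjects gather below 15, the lower stratum is a mixture and the upper stratum is almost entirely non-dialysed. A difference in treatment effect that belongs to dialysis would then appear, diluted, as an eGFR interaction in 2.4.8. The same holds in 3.1.3. There the events after the start of SYR-472 are shown with treatment groups pooled, so a dialysis-related difference in event rates has no concurrent control to set it against. The hemodialysis factor does not answer the remaining question, which is whether effect or safety differs between non-dialysed subjects below 15 and those at 15 or above.

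**Working it through.** **Plan's own figures.** The documents give no figure for the overlap of the two factors. The nearest figures are those in Protocol 13.3: difference 0.40%, SD 0.80%, two-sided 5%. A noncentral-t calculation gives n = 85.03, hence 86 per group for 90% power, and 70.56% power at 51 per group. Both match the protocol. The SD and the 51 per group are used in step 4.

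**1. When a dialysed subject falls below 15.** The SAP equation is eGFR = 194 × Cr^-1.094 × age^-0.287, times 0.739 for women. Because the result is rounded to an integer, below 15 means an unrounded value below 14.5. The creatinine at the boundary is

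Cr = (194 × age^-0.287 [× 0.739] / 14.5)^(1/1.094).

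For a man of 65: (58.5 / 14.5)^(1/1.094) = 3.58 mg/dL.

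| Age | Men | Women |
|---|---|---|
| 50 | 3.84 | 2.91 |
| 65 | 3.58 | 2.72 |
| 80 | 3.39 | 2.57 |

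At ages 50 to 80 and both sexes, creatinine 5 mg/dL gives eGFR 7.0 to 10.9, and 8 mg/dL gives 4.2 to 6.5. Whether dialysed subjects exceed these cut-offs is an assumption; the documents give no creatinine values for them.

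**2. Non-dialysed subjects can also fall below 15.** By Cockcroft-Gault, a 65-year-old man of 60 kg at Cr 3.58 has Ccr = 75 × 60 / (72 × 3.58) = 17.5 mL/min; at 70 kg it is 20.4. Both are well inside the entry limit of 30. Call q the share of non-dialysed subjects below 15. Assume Ccr uniform from L to 30, mean age 60-70, 25% women, and mean weights of 67 kg (men) and 57 kg (women). Then q is 53-60% for L = 5, 41-50% for L = 10 and 24-34% for L = 15.

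**3. How much of a dialysis difference the eGFR contrast carries.** Let h be the share on dialysis, all below 15 (assumed). The dialysed share of the lower stratum is p = h / (h + (1 - h)q). If the effect, or event rate, is D in dialysed and N in non-dialysed subjects whatever their eGFR, the lower stratum shows pD + (1 - p)N and the upper shows N. The eGFR contrast is therefore p(D - N). The two splits classify subjects alike in a proportion h + (1 - h)(1 - q).

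| h | q | p | Agreement |
|---|---|---|---|
| 0.3 | 0.2 | 68% | 86% |
| 0.3 | 0.6 | 42% | 58% |
| 0.5 | 0.2 | 83% | 90% |
| 0.5 | 0.4 | 71% | 80% |
| 0.5 | 0.6 | 62.5% | 70% |
| 0.7 | 0.2 | 92% | 94% |
| 0.7 | 0.6 | 80% | 82% |

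If only a share s of dialysed subjects is below 15, the carried share is the dialysed fraction of the lower stratum minus that of the upper. For h = 0.5, q = 0.4, s = 0.9: 0.45/0.65 - 0.05/0.35 = 0.69 - 0.14 = 0.55, instead of 0.71. It reaches zero only when s = q.

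**4. Cell sizes with three levels.** With 2 × 51 = 102 evaluable subjects and h = q = 0.5 (assumed), about 51 are on dialysis and about 25 or 26 fall in each non-dialysed cell, or roughly 13 per arm. The 95% CI half-width is 2.06 × 0.80 × √(2/13) = 0.65% HbA1c.

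**The case against.** The other side has real points. Hemodialysis is its own factor in both lists, so a reader can set any eGFR difference beside the dialysis result, and the non-dialysed stratum is reported directly. That stands, but it does not split non-dialysed subjects at 15, which is the only thing an eGFR factor could add. Protocol 4.2 presents dialysed subjects as the far end of one renal-function series (AUC ratios 1.56 to 3.68), so the lowest eGFR class is not an absurd place for them. Yet that series lists severe impairment without dialysis and dialysis as separate groups.

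The Handling Rules for Analysis Data are not among the documents and might make eGFR ineligible in dialysed subjects. If so, the SAP's strata do not show it. SAP 2.4.5 makes all efficacy analyses beyond the primary one supportive or exploratory, and the repaired cells are imprecise: a half-width of 0.65% against an assumed effect of 0.40%. Both points limit the weight of the concern.

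A reader might infer that nearly all dialysed subjects fall below 15 and that the eGFR result mostly repeats the hemodialysis contrast. The documents do not support that. They give no creatinine values and no planned dialysis share, and entry sets no lower limit on Ccr. At the low end of the range 58% of the lower stratum is not dialysed.

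A reader might also infer that HbA1c reading low on dialysis (justification of criterion 4 in Protocol 7.1) would itself surface as an eGFR effect. A low level affects both randomised arms. It creates a treatment-by-stratum interaction only if it also alters the between-arm difference in change, which nothing in the documents shows.

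**Conclusion.** The point holds as one of confounding whose degree is unknown. The SAP applies a creatinine equation to dialysed subjects without exception and does not separate the eGFR factor from dialysis. If dialysed subjects fall mostly below 15, the contrast cannot be read as an effect of renal function. With 30-70% on dialysis, all below 15, and 20-60% of the others below 15, it carries about 42-92% of any purely dialysis-related difference. These shares are assumptions, and the figure falls if some dialysed subjects are at 15 or above. The consequence is confined to exploratory efficacy and descriptive safety subgroups; the primary analysis and the 70.6% power do not change. This is a cheap improvement in interpretability.

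**What to change.** In SAP 2.4.8 and 3.1.3, replace the two-level eGFR factor with three levels: hemodialysis; no hemodialysis with eGFR below 15; no hemodialysis with eGFR 15 or above. If the Handling Rules already exclude eGFR in dialysed subjects, state that in the SAP and label the factor accordingly. Applying the same split to the eGFR row of the baseline table (1.2.1) is optional, since hemodialysis is already shown there.

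The cost is wording and table shells; hemodialysis status and eGFR are already collected. The downside is small non-dialysed cells, about 13 per arm under the split in step 4, so the estimates should be presented as descriptive. If all dialysed subjects are below 15, the upper stratum keeps its present size and only the lower one is divided.
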